#### Safety Evaluation:

Standard safety procedures during synthesis and injection of the tracers will be followed. This will be monitored by the radioactive drug research committee at Washington University. Those measures are implemented and monitored by the FDA and the local radioactive drug research committee to ensure the drugs are pyrogen free, and that the dose is properly measured, etc. Injection of the tracer is done under the supervision of a physician and could

entail monitoring for vitals, cardiac rhythm, etc. Please see the Washington University Supplemental Imaging Protocol for further details.

# Safety Management:

Adverse events will be monitored at the time points specified in the schedule of events and reported to the PI and the IRB, as required per policy. During the PET/CT, patients will be under the care of [name] at Washington University. Following the PET/CT, patients can contact [name] / Mercy Research team. If an unanticipated problem occurs, study team will notify Mercy IRB, Washington University study team and Washington University IRB, and the radioactive drug research committee or FDA, as applicable.

All related, serious adverse events will be followed until resolution or stabilization as evaluated by the Principal Investigator.

#### Definition of an Adverse Event

Definitions of adverse events, serious adverse events and unanticipated problems per Mercy policies and procedures. Serious adverse events and unanticipated problems related to the PET/CT scan and tracer injection will be documented and reported for this study. Adverse event screening will begin at the beginning of visit 2 through 30 days following the ablation procedure.

#### Adverse Event Reporting (Mercy and Washington University)

If unanticipated problems related to the research involving the risks to subjects or others occur during the course of the study, these will be reported to the Mercy IRB in accordance with Institutional Review Board policies and to the Washington University study team for reporting to the Washington University Institutional Review Board, Human Research Protection Office and/or Radioactive Research Drug Committee, as applicable. Adverse events that are not serious but that are notable, in the opinion of the Principal Investigator, and could involve increased risks to subjects will be summarized and submitted to the IRB at the time of continuing review.

#### Data Management:

Data will be maintained by Mercy Research according to Mercy and Mercy Research policies and procedures. Case Report Forms will be stored on secured computers.

Data will be stored at a Mercy Research office at Mercy Hospital St. Louis.

Investigators will have access to data / images.

Data will be shared between investigators. Unidentified data could be used for publication in peer review journals, etc.

Images and study data will be shared with Washington University investigators. Data of interest from CRFs for completed subjects will be entered into an Excel spreadsheet at the end of the study to create a study dataset to be shared with Washington University investigators. The study dataset will be sent via Mercy Secure File Transfer system. Images may be accessed by the Mercy Principal Investigator using the Washington University Central Neuroimaging Data Archive (CDNA) and may be shared amongst the Washington University and Mercy study teams for analysis in a secure manner, via the Washington University CDNA system, secure email or CD through mail or hand delivery. PET/CT images will not be loaded into patient medical records.

Confidentiality and Privacy:

All data and records generated during this study will be kept confidential in accordance with Institutional policies and HIPAA and subject privacy.

The investigators and other research personnel will not use such data and records for purposes other than study conduct.

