# Schedule of Events

Procedures	Screening /Visit 1	Optional Cardiac MRI*	Visit 2**	Visit 3	Data-only Follow-up (30 days)
Informed Consent	X				
Demographics	X				
Past Medical History	X				
Inclusion / Exclusion	X				
criteria review					
PET/CT Scan			X**		
Ablation				X	
MRI		X			
Adverse Events			X**		X
Assessment					

\* Cardiac MRI will be done as per standard of care prior to ablation of ventricular tachycardia. Cardiac MRI is not required for participation on the study.

Criteria for withdrawal of subjects and provision of care after withdrawal

- Patients may cancel participation in the study at any time without penalty. Clinical care will be provided as per standard of care.
- Patients will be removed from the study if they become ineligible at any point before or after the PET scan is performed, or if they become unable or are no longer willing to provide informed consent.

\*\* Visit 2 occurs at Washington University. Mercy PI/Mercy Research will be notified by Washington University of any adverse events occurring during Visit 2

- The investigator(s) may also discontinue or remove a participant from the study for the following:
  - o To protect the subject for reasons of safety.
  - If any clinical adverse event, laboratory abnormality, or other medical condition or situation occurs such that continued participation in the study would not be in the best interest of the participant.
  - The subject is determined no longer be able to complete study protocol visit activities.
  - Significant non-compliance by the subject with study requirements.
- The reason for participant discontinuation or withdrawal from the study will be documented.
- It will be documented whether each subject completes the study.
- Information collected up to the last visit will be included in analysis.
- Subjects who sign the informed consent but do not complete the PET/CT scan may be replaced as enrolled subjects.
- Participants who sign the informed consent form and complete the PET/CT scan and subsequently withdraw or are withdrawn or discontinued from the study will not be replaced as enrolled subjects.
- Participants who are unable to complete the PET/CT will be considered withdrawn/incomplete. Their data will be included in summary analysis but will not be used in hypothesis testing.

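### Does limiting the shared dataset to completed subjects drop participants whose PET/CT failed from the summary analysis?

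*Protocol*

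**What the plan says.** Two places in the protocol bear on this.

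- **Withdrawal criteria (under Schedule of Events).** "Participants who are unable to complete the PET/CT will be considered withdrawn/incomplete", and the next sentence reads "Their data will be included in summary analysis but will not be used in hypothesis testing". For withdrawals in general, "Information collected up to the last visit will be included in analysis". Completion is recorded person by person: "It will be documented whether each subject completes the study". On replacement, "Subjects who sign the informed consent but do not complete the PET/CT scan may be replaced as enrolled subjects", whereas those who "complete the PET/CT scan and subsequently withdraw or are withdrawn or discontinued from the study will not be replaced as enrolled subjects".
- **Data Management.** "Data of interest from CRFs for completed subjects will be entered into an Excel spreadsheet at the end of the study", the purpose being to "create a study dataset to be shared with Washington University investigators". The same section says that Mercy Research maintains the data and keeps the CRFs on secured computers, and that investigators have access to data and images.

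The Brief Protocol adds that missing the follow-up visit does not stop a patient counting as complete. It does not say the same of missing the scan.

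**The concern.** Under the protocol's own label, a participant whose scan failed is incomplete, so on a literal reading that person is not a completed subject and gets no row in the spreadsheet. This is the only dataset whose construction the protocol describes. The Analysis section keeps the electroanatomic data off the CRFs, so a CRF-based file would chiefly serve descriptive summaries: demographics, history, completion status and adverse events. Those are the summaries in which the withdrawal criteria promise to include these participants.

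The people left out would not be a random subset. The Subject Payment section foresees technical or quality failures of the scan, and replacement is allowed, so the file could show 15 clean scans and no failures although Study Goal A concerns the capability to produce and use the tracer. Adverse-event screening starts at the beginning of Visit 2 (Definition of an Adverse Event), so a participant whose scan was stopped by an event would have safety data but no row. Participants who withdraw after the scan might be lost too, depending on how completion is read.

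**Working it through.** The protocol gives no figure to reproduce here: it states no scan-failure rate, no feasibility rate and no derivation of the 15 patients. The check is mainly one of text.

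**1. What each rule governs**

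| Question | Withdrawal criteria | Data Management |
|---|---|---|
| What is being decided? | Whose data enter the analyses | What goes into a file sent to the imaging site |
| Participants unable to complete the PET/CT | In the summary, out of hypothesis testing | Not in the file, on the strict reading of completed |
| Source of the summary analysis | Not specified | Not specified |

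The two rules contradict each other only if the summary has to be produced from the shared file. Neither section says so. With the CRFs for all participants at the enrolling site, the analyst can include everyone in the summary and send a narrower file.

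**2. Whether information is lost**

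Visit 2 takes place at Washington University, which is also the recipient of the file. Under the Schedule of Events footnote that site notifies the enrolling site of Visit 2 adverse events. Under Safety Management it has care of the patients during the scan, and under Subject Payment it pays those whose scan fails for technical reasons. Scan failures and Visit 2 events are therefore known at both sites. Baseline data and post-scan events stay on the enrolling site's CRFs. The reporting routes in Safety Management and Adverse Event Reporting do not depend on completion status.

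**3. What completed may mean**

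The Analysis section speaks of evaluation once all participants have completed the study, which can be read as the end of participation. The Data Management entry also happens at the end of the study. On that reading nobody is omitted. The incomplete label in the withdrawal criteria favours the stricter reading but does not settle the matter.

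**4. Size on the strict reading (assumed counts)**

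Let k be the number of failed scans, all replaced, and w the number of later withdrawals not counted as completed, with 15 completed scans. The share of those scanned or attempted that is absent from the file is (k + w)/(15 + k).

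| k | w = 0 | w = 1 |
|---|---|---|
| 1 | 1/16 = 6.25% | 2/16 = 12.5% |
| 2 | 2/17 = 11.8% | 3/17 = 17.6% |
| 3 | 3/18 = 16.7% | 4/18 = 22.2% |

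If one of 16 participants had an event that stopped the scan, the file would show 0/15 and the full population 1/16 = 6.25%. The exact (Clopper-Pearson) 95% intervals are:

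- 0/15: 0 to 1 − 0.025^(1/15) = 0.218, that is 0% to 21.8%.
- 1/16: 0.2% to 30.2%.

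These figures describe the shared file. They would describe a reported result only if a table were drawn from that file against the withdrawal criteria.

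**The case for a change.** The strongest case for a change is that both rules are already written and use the same vocabulary in opposite directions, so this is not detail left for an SAP. Completion is a documented status that differs between participants, and the group labelled incomplete is the very group that must be summarised. The file is called a study dataset and no other is described, so someone may well tabulate from it. In a study of 15, one missing row is visible. The repair would be one phrase plus a status and reason that the protocol already requires to be documented.

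What stands is that the wording is loose, that a careless analyst could use the wrong file, and that a clarification would cost almost nothing. What does not stand is the step from there to an unsupported summary. It assumes a link between file and summary that the text does not make, and an analyst following the withdrawal criteria would include these participants. Nor is a scan-completion rate of 100% built into any result, because Goal A states no rate or denominator and nothing says that one would be counted from this file.

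The narrower file also has a reason. Participants without a PET/CT are excluded from hypothesis testing in any case, so a file for joint imaging work does not need them, and leaving them out limits disclosure to a second institution. The obvious rewording, to cover everyone who reached Visit 2, would not fully match the withdrawal criteria either: a consented participant who became unable to be scanned before Visit 2 would still have no row.

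**Conclusion.** No change to the plan is called for. The two sections sit awkwardly together but can both be followed: the summary analysis covers participants without a completed PET/CT, as the withdrawal criteria require, and the file shared with the imaging site may be narrower. On the strict reading, and with an assumed 1 to 3 failed and replaced scans, that file would lack 6.25% to 16.7% of those scanned or attempted, or 12.5% to 22.2% if one later withdrawal is also left out. The protocol supplies none of these counts, and no stated result, safety report or feasibility figure depends on them.

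This conclusion rests on two conditions: that the CRFs of incomplete participants are kept at the enrolling site, as Data Management provides, and that the summary is run under the inclusion rule in the withdrawal criteria. If the sponsor edits the section for other reasons, it could say that the summary is run from the CRFs, or that the dataset carries all consented participants with completion status and reason, with only a count and reasons sent for those who declined the imaging site's consent. That is optional tidying.

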# **Preliminary hypothesis:**

1) PET/CT imaging with [C-11] MHED can guide the identification of elements that are critical to the development of VT, which exhibit abnormal sympathetic influence.

Areas of relative increase in myocardial [C-11] MHED uptake may represent regional nerve sprouting within the background of dysinnervated scar and? represent critical elements to the substrate of VT.

2) Ablation targets detected by conventional electrophysiologic mapping techniques are likely to exist in such areas with dysinnervation, which are likely representative of nerve sprouting.

The data provided by PET/CT imaging could be used to modify the current approaches for VT ablation. Data on the regional adrenergic receptor quantity and distribution could be crucial to improving procedural outcomes and event-free survival in patients with life threatening ventricular arrhythmias.

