# **Brief Protocol:**

# Study Design:

Pilot, hypothesis generating, nonrandomized study

Number of subjects: 15 patients

Duration of subject participation: Subjects will be enrolled in the study during a pre-ablation visit/consultation and participate in the study from the time consent is obtained, through the PET scan, and for 30 days following ablation. Patients are not required to attend the follow-up visit in order to be considered complete in the study.

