#### Subject Recruitment:

Mercy clinic patients will be recruited by the Principal Investigator, Sub-Investigators, or other designated study team member. Informed consent will be obtained by the Principal Investigator or delegated study personnel. After the informed consent is obtained, the study team will provide the subject's information to the Washington University coordinator for scheduling of the PET/CT scan using the Study Subject Information Sheet by Mercy Secure File Transfer System.

Study Procedures:

Screening/Visit 1	Standard of Care + Research	Discuss ablation and its clinical indication Discuss participation in the study Obtain informed consent Determine eligibility
Optional Cardiac MRI	Standard of Care	Cardiac MRI will be done as per standard of care prior to ablation of ventricular tachycardia. Cardiac MRI is not required for participation on the study
Visit 2	Research	PET/CT scan will be done at Washington University imaging facility up to 21 days before scheduled ablation.
Visit 3	Standard of Care	Cardiac ablation procedure will be done per standard of care
Data-only follow-up	Research	Adverse event and VT recurrence data, when available, will be collected 30 days (+/- 5 days) following cardiac ablation procedure.

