## Electroanatomic mapping procedure:

Electroanatomic maps will be created using mapping catheters as performed for standard of care ablation procedures.

High-density electroanatomic maps (>150 points for the LV) will be acquired using the Thermocool SmartTouch or Thermocool SF catheters or similar mapping catheters.

The areas of interest will be mapped in detail using conventional electrophysiologic techniques. Signal amplitude, electrogram characteristics (low amplitude, late, fractionated, etc.) will be noted. Entrainment mapping of VT will be pursued whenever possible.

Maps will be merged offline after the ablation case has ended, which is typically done on the mapping computers. Correlations between PET uptake values and electro-anatomic data obtained during ablation (data regularly obtained during the course of an ablation case including refractory periods, voltage measurements, roles in VT circuit) will be made as part of final data analysis.

Post-procedural follow up will be arranged for subjects based on current standards of care. Antiarrhythmic drugs will be required for, at least, the first 8 weeks unless there is a contraindication.

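### The protocol does not withhold the MHED PET images from the ablation operator until targets are recorded, so the independence of targets from uptake that hypothesis 2 needs is unprotected

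*Protocol*

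**What the plan says.** - **Hypothesis** (Protocol, Preliminary hypothesis, item 2): "Ablation targets detected by conventional electrophysiologic mapping techniques are likely" to lie in dysinnervated areas thought to reflect nerve sprouting. Goal C in Study Goals passes such correlations on to larger studies.
- **Order of events** (Subject Recruitment, Study Procedures table): "PET/CT scan will be done at Washington University imaging facility up to 21 days before scheduled ablation".
- **Access** (Data Management): "Investigators will have access to data / images", and "Images may be accessed by the Mercy Principal Investigator using the Washington University Central Neuroimaging Data Archive (CDNA"). The same sentence lets the two study teams share images for analysis through the archive, secure email or CD. The section also keeps the images out of the medical record.
- **Mapping** (Electroanatomic mapping procedure): "The areas of interest will be mapped in detail using conventional electrophysiologic techniques". Entrainment is used where possible, and a left ventricular map needs more than 150 points.
- **Later steps**: "Maps will be merged offline after the ablation case has ended" (same section). The Analysis section places fusion at the end of the study and evaluation of the electroanatomic data after every participant has finished.
- **Scale** (Study Design): "Pilot, hypothesis generating, nonrandomized study"; "Number of subjects: 15 patients".

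**The concern.** The comparison in hypothesis 2 is informative only if its two sides are obtained independently: uptake from the scan, and targets from electrophysiology alone. Here the scan exists before the targets are chosen, and nothing in the protocol keeps it from the person choosing them. If knowledge of uptake influences where points are taken or lesions placed, part of any overlap between targets and uptake is produced by the procedure rather than by the disease.

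This cannot be repaired later. Blinding the offline reader to uptake protects the classification of targets already recorded. It does not recover sites that were never sampled because attention was elsewhere. The safeguard therefore belongs in the conduct of the ablation visit, not in an analysis plan.

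**Working it through.** No stated figure is at issue. The only design number is the 15 participants, given without a power or precision calculation, so there is nothing to reproduce. The check is to put the steps in order and ask what each safeguard delays.

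**Sequence in the protocol**

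1. PET/CT scan: 0 to 21 days before ablation.
2. Ablation with conventional mapping, as standard of care.
3. Merging of maps: offline, after the case.
4. Fusion, target classification and correlation: end of study.

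Image access is not tied to any of these steps. Data Management does date another transfer: the spreadsheet built from the case report forms is created and shared at the end of the study. The image provision carries no such date.

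**What each safeguard restricts**

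- *Merge after the case; fusion and evaluation at the end.* These delay the combined map and the analysis. The unfused PET/CT can be viewed as soon as it is available.
- *Sharing for analysis.* This states a purpose for exchange between the teams, but sets no date.
- *Images kept out of the medical record.* This closes one route. Archive, email and CD remain.
- *Standard-of-care ablation and conventional techniques.* These fix the method, not the location of points. The regions to be mapped in detail are left to judgement, and the 150-point minimum is a total with no rule on distribution.

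None of the four prevents the operator from seeing uptake before choosing targets.

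**Can the bias be sized?** Suppose raised-uptake areas make up a share p of scar, targets are truly unrelated to uptake, and those areas are sampled at k times the density of the rest. The share of targets falling there is pk / (pk + 1 − p). With an assumed p = 0.20:

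- k = 1: 0.20 / 1.00 = 20%
- k = 1.5: 0.30 / 1.10 = 27%
- k = 2: 0.40 / 1.20 = 33%

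The odds of a target lying in the area are pk / (1 − p), against p / (1 − p) without steering, so the apparent odds ratio is k for any p. The output is the assumed input. The protocol gives neither p nor k, so this shows the direction of the bias and does not estimate its size.

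**Which targets are exposed?** The proportional model requires that more sampling yields proportionally more targets. That is plausible for the third category in the Analysis section, abnormal local electrograms with no assigned circuit role. It fits the first two poorly: isthmus and entrance or exit sites are roles in a circuit, and extra points do not create such a role where none exists.

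**The case against.** The strongest reply is that the protocol, read as a whole, describes an observational scan that does not steer the index procedure. Ablation follows standard of care, mapping is conventional, merging and analysis come afterwards, sharing is for analysis, data use is confined to study conduct, and Potential Benefits to Subjects speaks of guidance for future procedures. An operator who deliberately mapped by uptake would depart from that description. This stands, and it limits the concern mainly to unconscious influence. It does not remove it, because none of these statements delays viewing.

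A reader might infer more than the text supports:

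- *That images will be opened before or during ablation.* No section says so. The protocol is silent on timing, and nothing supports viewing during the case.
- *That the Principal Investigator is the operator.* The protocol does not say who performs the ablations. Access for investigators generally leaves the possibility open without establishing it.
- *That no restriction exists anywhere.* The PET/CT and Safety Evaluation sections refer to a Supplemental Imaging Protocol that is not shown and may govern release of images.
- *That the whole pilot is compromised.* Goal A, producing and using the tracer, is unaffected. For Goal B, denser sampling does not by itself change the voltage or refractory period measured at a site. The exposed part is the target-uptake association in hypothesis 2, which the protocol calls preliminary and which supports no confirmatory test.

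**Conclusion.** The gap is real but narrow. The protocol gives investigators untimed access to images that precede the ablation and blinds no operator, so it does not protect the independence of targets from uptake. The possible consequence is an inflated or otherwise distorted target-uptake association, chiefly among abnormal local electrograms without a circuit role. Its size cannot be derived from the document, and no odds ratio should be attached to it.

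The conclusion assumes that at least one person with image access performs or directs mapping, and that the Supplemental Imaging Protocol does not already withhold the images. Neither can be confirmed here, so confidence is moderate. In a 15-patient hypothesis-generating pilot this is an inexpensive improvement worth making, because the correlations are meant to inform later studies and the bias cannot be removed once the maps are recorded.

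**What to change.** In Electroanatomic mapping procedure and in Data Management, state that anyone performing or directing the mapping and ablation has no access to a participant's PET emission images or uptake readings until that participant's electroanatomic map, point tags and ablation tags have been saved and locked. Release access case by case after that. Provide a separate route for communicating incidental safety findings from the scan. Record any viewing before the lock, and show the target-uptake association with and without those cases. If the Supplemental Imaging Protocol already contains such a restriction, a cross-reference in Data Management is enough.

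The restriction need not cover investigators who take no part in mapping or ablation. The cost is protocol wording, a log entry and a delayed archive permission. An investigator who also operates waits up to 21 days, about three weeks, to see the images. No planned procedure is lost, since merging already follows the case.
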